
Characteristics of the Study Population

Target population

Adult subjects aged 65 or older with overactive bladder undergoing treatment with medication

Subjects enrolled by Penn Researchers

80

Subjects enrolled by Collaborating Researchers

0

Accrual

Recruitment/Retention Experience: The urogynecology/urology clinics of the Hospital of University of Pennsylvania are high volume referral clinics staffed by four urogynecologists and one urologist. We see 125 female and 50 male patients with OAB per month with eligibility:participation ratio of 1.5:1 in clinical trials. In recent trials, 50% of recruited adults were Caucasian and 45% African-American. We anticipate that the female:male ratio will be 2:1. Sample Size: Specific Aim 1: A sample size of 68 evaluable subjects will provide 90% power to detect a correlation coefficient of 0.72 or greater, assuming a correlation coefficient of 0.5 or less between the physical activity questionnaires and the criterion standard (accelerometer) is undesirable (null hypothesis). Assuming a 15% loss to follow-up, we plan to enroll 80 patients to ensure an adequate sample of at least 68 subjects with complete datasets. Specific Aim 2: We have conservatively assumed that 50% subjects will express preference for medication. Prior Penn studies show 56% adherence at 8 weeks in unselected subjects. Assuming that adherence will be 80% in subjects expressing preference for medication, a sample size of 80 subjects will provide 90% power to demonstrate a 30% difference in adherence rates in subjects who do or do not have preference for medication. Specific Aim 3: Assuming two-tailed alpha of 0.05, a sample size of 80 subjects will provide 90% power to show a 30% difference in physical activity in the proportion of subjects expressing preference for medication versus those without preference.

Key inclusion criteria

Inclusion Criteria: adults aged 65 or older, urinary urgency of quite a bit severity or more on the Overactive Bladder Questionnaire-Short Form (OABq-SF),⁵⁰ who are eligible for pharmacologic therapy for overactive bladder

Key exclusion criteria

Exclusion Criteria: predominant stress incontinence (on UDI-6), current/recent use (6 m) or contraindication to anti-cholinergic medication, severe voiding difficulties, men on 5-alpha reductase inhibitors, severe neurologic disease, recent anti-incontinence or prolapse surgery, other urinary tract conditions such as calculus or recurrent UTI.

Vulnerable Populations

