Analysis Plan Specific Aim 1 and 2: We will evaluate physical activity, adherence, and neurocognitive function before and after treatment to examine changes from baseline to 8 weeks in subjects with and without preference for medication. Concurrent validity, the relationship of the instrument to other similar evaluations, will be measured by comparing IPAQ, and CHAMPS scores to accelerometer data at baseline using the Spearman correlation coefficient and the intraclass correlation coefficient. Specifically, we will compare energy expenditure in MET*min/week (IPAQ) or MET*hour/week (CHAMPS) to that measured by the Actigraph accelerometer over the course of a week. For preference, we will compare subjects scores as indicated on the bidirectional scale to their necessity-harm differential as calculated by the Belief Screen of the BMQ using Spearman correlation coefficient. Contingency analyses tables will be used to determine the sensitivity and specificity of the bidirectional preference scale and the necessity-harm differential (as calculated on the Belief Screen) that best discriminates between those with preference for medication and those without. Discriminant validity, the ability to distinguish between populations, will be determined by comparing mean differences in energy expenditure for each physical activity instrument between responders and non-responders to anticholinergic medication as defined by the PGI-I. We will compare total MET*min/week (IPAQ) or MET*hour/week (CHAMPS), as well as energy spent in sedentary and moderate-to-vigorous physical activities (CHAMPS) between responders and non-responders using Wilcoxon rank sum test. For preference, we will compare the BMQ Belief necessity-harm differential and bidirectional preference scale score using Wilcoxon rank sum test. Responsiveness, the ability of the instruments to detect clinically meaningful change, will be assessed. First, pretreatment energy expenditure and preference will be compared with post-treatment activity and preference scores, respectively, using the t-test. Next, effect size (change in mean score/SD of baseline) and standardized response mean (change in mean score/SD of the change) will be assessed. For both, values of 0.50.7 will be considered moderate responsiveness; 0.81, good; and 1, excellent. We will measure minimum clinically important difference (MCID); specifically, the smallest change in physical activity associated with clinically meaningful change in global rating scale (mean change in energy expenditure in subjects indicating a little better or greater in the global rating scale). Specific Aim 3: We will compare within subject change in physical activity from baseline to 8 weeks using the paired t-test. Improvement in physical activity will be defined as 15% increase in energy expenditure as compared to baseline. The effect of age, comorbidities, baseline activity, severity of cognitive impairment, BMI on physical activity will be examined using regression analysis. We will also compare change in activity, proportion of subjects

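### The 15% loss to follow-up is allowed for only under Aim 1; Aims 2 and 3 have 8-week outcomes yet claim 90% power on all 80 enrolled, and Aim 2 has about 75% at the 68 expected to remain

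*Combined protocol and SAP*

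**What the plan says.** All three calculations stand in the protocol under Accrual (Sample Size).

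- **Aim 1.** "A sample size of 68 evaluable subjects will provide 90% power to detect a correlation coefficient of 0.72 or greater", against a null correlation of 0.5. The dropout allowance follows at once: "Assuming a 15% loss to follow-up, we plan to enroll 80 patients", and its purpose is "to ensure an adequate sample of at least 68 subjects with complete datasets".
- **Aim 2.** Half the subjects are assumed to prefer medication. Adherence in unselected subjects is put at 56% at 8 weeks, and at 80% in those who prefer medication. With 80 subjects, 90% power is claimed for a 30% difference. No alpha and no dropout allowance are given.
- **Aim 3.** "Specific Aim 3: Assuming two-tailed alpha of 0.05", 80 subjects are said to give 90% power for a 30% difference in a physical-activity proportion between the preference groups. No base rate and no dropout allowance are given.

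The Analysis Plan sets the timing. Concurrent validity means "comparing IPAQ, and CHAMPS scores to accelerometer data at baseline using the Spearman correlation coefficient and the intraclass correlation coefficient". Adherence (pill count and MASRI) is collected only at the 8-week visit in the Instrument and Testing Schedule, and the Aim 3 activity outcome is change from baseline to 8 weeks.

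**The concern.** The allowance is attached to the one powered quantity that later dropout cannot reduce, and is missing from the two that it does reduce. The questionnaires and the first accelerometer week are complete at about the time treatment starts. Adherence and change in activity exist only for subjects who reach week 8.

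The plan therefore expects 68 subjects with complete data in one sentence and counts on 80 with 8-week outcomes in the next two. If the 90% figures are taken at face value, a null result on preference and adherence, or on preference and activity, would be read as stronger evidence of no effect than the study can give.

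**Working it through.** **1. Aim 1, the plan's own figure.** Inputs: null 0.5, alternative 0.72, 90% power. Alpha is not stated for this aim; 5% is assumed. Fisher z: n = ((z_alpha + z_power) / (atanh 0.72 − atanh 0.5))² + 3, with atanh 0.72 − atanh 0.5 = 0.9076 − 0.5493 = 0.3583.

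- One-sided 5%: n = (2.926 / 0.3583)² + 3 = 69.7; power at 68 is 89.3%. This reproduces the plan closely.
- Two-sided 5%: n = 84.8; power at 68 is 82.4%. This does not.
- Dropout: 68 / (1 − 0.15) = 80, as stated.

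**2. Subjects with 8-week outcomes.** 80 × 0.85 = 68. With the plan's 50:50 split on preference, that is 34 per group instead of 40.

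**3. Aim 2.** Inputs: 80% from the plan; 50% is 80% less the stated 30%, read as percentage points; two-sided 5% is assumed, as alpha is given only for Aim 3. Formula: power = Φ((d − 1.96·se0) / se1), where se0 = √(2·p̄(1 − p̄)/n), se1 = √((p1(1 − p1) + p2(1 − p2))/n), d = 0.30, p̄ = 0.65.

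- n = 40 per group: se0 = 0.1067, se1 = 0.1012; (0.30 − 0.2090)/0.1012 = 0.90; power 0.82.
- n = 34 per group: se0 = 0.1157, se1 = 0.1098; (0.30 − 0.2267)/0.1098 = 0.67; power 0.75.
- One-sided 5%: 0.89 at 40 per group and 0.84 at 34.
- For 90% power, two-sided, the same formula needs 52 per group, or 104 evaluable.

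Detectable difference at 34 per group with 80% in the preference group: try 43% in the other. p̄ = 0.615, se0 = √(2 × 0.615 × 0.385 / 34) = 0.1180, se1 = √((0.16 + 0.2451)/34) = 0.1092; (0.37 − 0.2313)/0.1092 = 1.27; power 0.90. So 90% power belongs to a difference of about 37 points, not 30.

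**4. Aim 3.** Same formula, two-sided 5% as stated, difference of 30 points. The base rates are assumptions.

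| Rates (assumed) | Power, 34 per group | Power, 40 per group |
|---|---|---|
| 35% v 65% | (0.30 − 1.96 × 0.1213)/0.1157 = 0.54, so 0.70 | (0.30 − 1.96 × 0.1118)/0.1067 = 0.76, so 0.78 |
| 10% v 40% | (0.30 − 1.96 × 0.1050)/0.0985 = 0.96, so 0.83 | (0.30 − 1.96 × 0.0968)/0.0908 = 1.21, so 0.89 |

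**The case against.** **The allowance is not out of place under Aim 1.** That aim also covers responsiveness, the minimum clinically important difference and discrimination by PGI-I, all of which need week 8. Baseline pairs can be lost too: the monitor is collected a week after the visit, and the Background names non-compliance as a limit of accelerometers. This stands. For Aim 1 the allowance is sensible, and for the baseline correlation merely conservative. It does not explain why Aims 2 and 3 have none.

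**A reader might infer that Aim 1 is limited to 68 subjects and that up to 12 usable baseline pairs (80 − 68) are discarded.** The documents do not support that. The figure is a planning floor, "an adequate sample of at least 68 subjects with complete datasets", and nothing confines the baseline correlation to those who reach week 8. The terms for evaluable and complete data are left undefined, which is a gap in wording and not an exclusion rule.

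**Aim 2 could be read more favourably.** If 56% is the average over two equal groups and one has 80%, the other has 2 × 56 − 80 = 32%, and power is about 0.99 at 34 per group. But that is a 48-point difference, and the plan claims 90% for 30. The opposite reading, 80% against 56%, gives 0.57 at 34 per group. A one-sided test nearly recovers 90% at 80 subjects (0.89), but the plan does not state one for Aim 2, and at 68 it still gives only 0.84.

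**All 80 might be analysed.** The Design section mentions intention-to-treat, but in the context of following subjects who switch drug. It gives no rule for scoring adherence or activity in those with no 8-week visit. Even if all 80 counted, two-sided power for Aim 2 would be 0.82.

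**Conclusion.** The point holds for Aims 2 and 3. By the plan's own 15%, their 8-week comparisons will have about 68 subjects, and the stated 90% power is not delivered. Aim 2 has about 0.75 (0.82 with no loss at all), so 7 points of the shortfall come from ignoring dropout and about 8 were missing already. Aim 3 has about 0.70 to 0.83 over the two base-rate pairs tried.

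This rests on equal preference groups, a 30-point absolute difference, a two-sided 5% test (assumed for Aim 2, stated for Aim 3) and, for Aim 3, assumed base rates. The Aim 1 calculation is not at fault here: its baseline correlation can use every subject with valid baseline data, and nothing in the plan says otherwise.

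**What to change.** Under Accrual (Sample Size), apply the 15% allowance to Aims 2 and 3 by restating their power, or the difference detectable with 90% power, at 68 evaluable subjects. State the alpha and the comparison rate for Aim 2, and the base rate for Aim 3, so that the figures can be checked. Enrolment stays at 80 and no new data are needed; the cost is a less favourable stated power, for example about 0.75 for 80% v 50% in Aim 2.

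Optional: add one sentence that the Aim 1 baseline correlations and intraclass correlations use every subject with valid baseline questionnaire and accelerometer data, whether or not they reach week 8. This only makes explicit what the plan leaves open.

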(Tzefos 2009, AHRP reference guide) Additionally, fesoterodine has been compared to tolterodine, and may show greater efficacy. (Tzefos 2009) In fact, fesoterodine tends to have low incidence of dry mouth, and moderate incidence of constipation compared to other anti-muscarinics, making it a well-tolerated and appropriate first choice for most patients.(Ellsworth 2014) Low CNS penetration may also potentiate fewer CNS side effects.(Ellsworth2014) Additionally, our previously presented data on the potential positive effects of anticholinergic medication on physical activity was collected using fesoterodine, so there is a precedent for using this anticholinergic in a study examining changes in activity and sedentary behavior. Therefore, fesoterodine, the drug used in this study, is an appropriate medication for routine and standard care of overactive bladder. Fesoterodine is being supplied by Pfizer for the use of this study. As part of routine clinical care at the urogynecology clinics of the University of Pennsylvania Health System, all patients receive a pelvic exam, measurement of post-void residual by bladder ultrasound, and administration of four urinary questionnaires as part of evaluation of urinary symptoms. The OABq-SF and the UDI-6 will be used to screen patients. Inclusion Criteria: adults aged 65 or older, urinary urgency of quite a bit severity or more on the Overactive Bladder Questionnaire-Short Form (OABq-SF),50 who are eligible for pharmacologic therapy for overactive bladder Exclusion Criteria: predominant stress incontinence (on UDI-6), current/recent use (6 m) or contraindication to anti-cholinergic medication, severe voiding difficulties, men on 5-alpha reductase inhibitors, severe neurologic disease, recent anti-incontinence or prolapse surgery, other urinary tract conditions such as calculus or recurrent UTI. Recruitment/Retention Experience: The urogynecology/urology clinics of the Hospital of University of Pennsylvania are high volume referral clinics staffed by four urogynecologists and one urologist. We see 125 female and 50 male patients with OAB per month with eligibility:participation ratio of 1.5:1 in clinical trials.42, 48, 51 In recent trials, 50% of recruited adults were Caucasian and 45% African-American. We anticipate that the female:male ratio will be 2:1. Recruitment : Pre-screening will occur at a patients routine visit, or via chart review following clinical care. If a patient appears to be eligible, they will be referred to the study coordinator to schedule a baseline visit. Patients of urogynecology or other referring geriatrics/urology/primary care practices may also self-refer for participation, as long as their medical records are available for eligibility determination. Baseline visit: At this visit, the trained coordinator will obtain informed consent, administer physical activity and other questionnaires (see Instrument and Testing Schedule below). Routine pre-treatment counseling on medical treatment, as well as counseling on additional non-medical (biofeedback, behavioral strategies, pelvic floor muscle training) and interventional treatments (neuromodulation), will also be provided. Then the coordinator will administer the Preference instrument on a bidirectional scale with 0 being undecided, and either extreme (5 or -5) being a strong preference for that particular treatment. The Short Physical Performance Battery (SPPB) test will also be performed with the oversight of trained personnel for safety. Accelerometers and instructions for wearing the accelerometer will be provided at that time. The monitor will be retrieved from the patient by a study coordinator or investigator 1 week later. Intervention: All subjects (irrespective of preference) will receive a 90-day supply of open label fesoterodine 4 mg per day. They will start medication 1 week after the baseline visit. After 4 weeks of treatment, dose may be increased to 8 mg over the telephone based on symptom report. This dosing regimen is direct alignment with clinical care. Change of prescription to another anti-cholinergic may occur during the study period, if determined necessary by the physician. Criteria that would warrant stopping fesoterodine include: - inability to tolerate common side effects, including dry mouth, dry eyes, and constipation - lack of satisfactory urinary symptom control on the highest dose of fesoterodine - immediate withdrawal in case of life-threatening side effects (uncommon, including angina, angioedema, diverticulitis, gastroenteritis, heat prostration, hypersensitivity reactions, irritable bowel syndrome, QT prolongation) Once withdrawn from fesoterodine, managing physicians would use their clinical judgment to switch the patient to another anti-cholinergic medication or switch to another class of medication (beta 3 agonist, or mirabegron). These patients would continue to be followed until after the 8 week follow-up visit, as the statistical plan will involve intention-to-treat analysis. The patients will continue to participate in the 8 week follow-up visit (including questionnaires and SPPB), regardless of whether or not they were switched to another medication. All adults will receive printed educational material on fluid modification, behavioral strategies, and Kegel exercises. 8 week follow up visit: One week prior, the study coordinator will once again provide subjects with accelerometers and instructions for wearing the accelerometer. At the 8 week visit, the patient will again complete self-administered physical activity, urinary symptoms, adherence, pill count, and neurocognitive instruments and tests with the oversight of a trained investigator (see Instrument and Testing Schedule below). The monitor will be retrieved from the patient by a study coordinator or investigator at the 8 week follow up visit. Instrument and Testing Schedule BASELINE VISIT: Urinary questionnaires (OABq-SF, UDI-6) Preference: Belief in Medication Questionnaire (BMQ), Bidirectional Visual Analogue Preference scale Physical activity:

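### Aim 2's stated 90% power for a 30% adherence difference is approached only one-sided, with no loss, at the most favourable split, and its inputs are not reconciled with the cited 56%

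*Combined protocol and SAP*

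**What the plan says.** All the planning figures are in the combined protocol and SAP, under Characteristics of the Study Population, Accrual, in the sample-size text for Specific Aim 2.

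- Preference share: "We have conservatively assumed that 50% subjects will express preference for medication".
- Background rate: "Prior Penn studies show 56% adherence at 8 weeks in unselected subjects".
- Preferrer rate: "Assuming that adherence will be 80% in subjects expressing preference for medication".
- Claim: "a sample size of 80 subjects will provide 90% power to demonstrate a 30% difference in adherence rates" between subjects with and without a preference for medication.

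The Aim 2 text gives no alpha, no sidedness, no adherence rate for non-preferrers and no evaluable number, and does not say whether the 30% is absolute or relative. Alpha is stated only for the next aim: "Specific Aim 3: Assuming two-tailed alpha of 0.05, a sample size of 80 subjects will provide 90% power". A 15% loss to follow-up, taking 80 enrolled to 68 evaluable, is stated for Aim 1 and not carried into Aim 2. The Objectives section words the Aim 2 hypothesis directionally (higher adherence in preferrers). Preference is observed, not allocated; under Study Design, "All subjects (irrespective of preference) will receive a 90-day supply of open label fesoterodine 4 mg per day".

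**The concern.** Two things look wrong.

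First, 90% looks high for 80 subjects split evenly and a 30-point gap, and the text omits what a reader needs to check it.

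Second, unselected subjects are a mixture of preferrers and non-preferrers, so their adherence rate should be the weighted average of the two group rates. The stated share, preferrer rate and gap do not average to 56%.

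Aim 2 tests the preference instrument's construct validity through adherence, and Aim 3 then uses the instrument as validated. If adherence does not differ detectably between the groups, the stated power decides how that is read. A null result presented as coming from a 90%-power comparison would be over-interpreted if the power for the stated difference is nearer 77%.

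**Working it through.** **Inputs.** From the Aim 2 text: N = 80, preference share f = 0.50, preferrer rate 0.80, difference 30%, background rate 0.56. From the Aim 1 text: 15% loss, 80 × 0.85 = 68. My assumptions: alpha 5%, run both one- and two-sided because Aim 2 states neither, and a pooled z-test of two proportions because no test is named for this calculation. Power is by exact enumeration of the two binomials unless marked approximate.

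**1. Reproducing the 90%.** Take 30 points, so 80% v 50% at 40:40. The normal approximation is Φ((0.30 − z·SE0)/SE1), with

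- SE0 = √(0.65 × 0.35 × 2/40) = 0.1067
- SE1 = √((0.8 × 0.2 + 0.5 × 0.5)/40) = 0.1012

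Two-sided: (0.30 − 1.96 × 0.1067)/0.1012 = 0.90, power 81.6% (exact 81.7%). One-sided: (0.30 − 1.645 × 0.1067)/0.1012 = 1.23, power 89.1% (exact 89.4%). So the stated figure is nearly recovered one-sided with all 80 evaluable, and not two-sided. Fisher's exact test is lower: 74.9% and 83.7%.

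**2. Applying the plan's own loss and the other reading of 30%.** Since 0.56/0.80 = 0.70, 56% is exactly 30% below 80% in relative terms, so 80% v 56% is a possible reading.

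| Rates | Split | Two-sided | One-sided |
|---|---|---|---|
| 80% v 50% | 40:40 | 81.7% | 89.4% |
| 80% v 50% | 34:34 | 76.8% | 84.8% |
| 80% v 56% | 40:40 | 63.8% | 76.4% |
| 80% v 56% | 34:34 | 58.9% | 70.0% |

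By the approximate formula, 90% power for 80% v 50% at an even split needs 52 per group (104 evaluable) two-sided, or 42 per group (84 evaluable) one-sided.

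**3. Do the inputs average to 56%?** Overall rate = 0.80f + p(1 − f), with p the non-preferrer rate.

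- f = 0.50, p = 0.50: 0.40 + 0.25 = 65%, not 56%.
- Keep 80%, 50% and 56% and solve for f: (0.56 − 0.50)/0.30 = 0.20. The split is 16:64 and power is 60.8% two-sided, 74.1% one-sided, with no loss.
- Keep f = 0.50, 80% and 56% and solve for p: (0.56 − 0.40)/0.50 = 0.32. The gap is 48 points and two-sided power is 99.6% at 40:40, 98.7% at 34:34.

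The same mismatch therefore lowers power under one repair and raises it under the other.

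**4. Is 50% conservative?** For 80% v 50% with 80 evaluable, two-sided:

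| Share preferring | 20% | 30% | 50% | 70% | 80% |
|---|---|---|---|---|---|
| Power | 60.8% | 74.0% | 81.7% | 77.4% | 66.0% |

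An even split is about the most favourable, so any clear imbalance lowers power.

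**The case against.** The strongest defence is that the 90% calculation never uses the 56%. It needs only the split and 80% v 50%, the hypothesis is directional, and one-sided with all 80 evaluable it comes out at 89%. That stands as far as it goes. But the sidedness is not documented, the neighbouring aim states a two-tailed test, and the loss assumed in the same section brings even the one-sided figure to 85%.

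A reader might infer that the figures contradict each other, that only 20% can prefer medication, and that the 90% fails for that reason. The documents do not support this. The 56% is reported from prior studies and is not declared to be the expected overall rate here. The prior adherence studies described in the protocol enrolled women, while this cohort is aged 65 or older and expected to be about one-third male, so 65% overall is not ruled out. And if 56% is held, letting the non-preferrer rate give way puts power above 98%.

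A reader might also infer that the sample will lean towards medication because everyone enrolled accepts free drug. That is plausible but undocumented: treatment is given whatever the preference, after counselling on non-drug options. The documents show only that the split is outside the investigators' control.

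Finally, *conservatively* may mean only a low guess at the share. It still misleads in a power statement.

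**Conclusion.** The point holds as a defect of statement and of the power quoted for a 30-point difference. At 50:50 and 5%, power for 80% v 50% is 82% two-sided or 89% one-sided with no loss, and 77% or 85% at 68 evaluable. On the relative reading it is 64% or 76% with no loss. The 90% is approached only with a one-sided test, no loss and an even split together.

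Separately, the 56% is unreconciled with the 65% that the other inputs imply. That calls for an explanation; it does not by itself show the power to be too high, because the direction depends on which input changes.

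The figures rest on 5% alpha, a pooled z-test, and subjects lost to follow-up not counting as evaluable for adherence; the plan gives no rule for counting them otherwise. The enrolment target is unaffected, since 80 is derived from Aim 1.

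**What to change.** Revise the Aim 2 sample-size text only:

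- Delete *conservatively*.
- State alpha, sidedness, the test, the non-preferrer rate, and whether the 30% is absolute or relative.
- Either choose a share and two group rates that average to 56%, or say why this cohort should differ from the prior studies. If the 50% share and 80% are kept with 56% overall, justify the 48-point gap this requires.
- Restate power at 68 evaluable: for 80% v 50% at 50:50, about 77% two-sided or 85% one-sided.
- Add a short table of power over preference shares from 20% to 80%.

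The cost is wording. Enrolment stays at 80 and no procedure changes. The downside is a less favourable stated power for the 30-point difference.

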Our primary objective is to show that treatment preference and physical activity can be measured using patient-reported instruments. We also hypothesize that preference for anti-cholinergic medications is associated with higher adherence and improvement in domains relevant to falls in adults with OAB, including urgency, physical activity, and balance. Finally, we plan to show that treatment of urgency urinary incontinence with anti-cholinergic medication does not worsen neurocognitive function relevant to falls. Specifically, the overriding goal of this proposal is to validate patient-reported instruments that measure physical activity and preference for medication in elderly adults with overactive bladder, and examine the effect of treatment on physical activity and risk for falls (fall efficacy) in adults who prefer medication for the treatment of overactive bladder. Specific Aim 1: To determine the construct validity and responsiveness of physical activity instruments in older adults undergoing treatment for overactive bladder. We hypothesize that physical activity levels as measured by questionnaires will correlate with physical activity as measured by accelerometer. We will measure responsiveness of the instruments by comparing change in physical activity levels before and after treatment of OAB. The results will be informative as to which, if any, instrument is useful for measuring physical activity in adults with OAB. Specific Aim 2: To determine the construct validity of an instrument to measure preference for medication in older adults undergoing treatment for overactive bladder. We hypothesize that adults with preference for medication will have higher adherence to treatment at 8 weeks than adults who do not prefer medication. The results will enlighten us to which, if any, instrument, is useful for measuring preference for treatment with anti-cholinergic medication in adults with OAB. Specific Aim 3: To use the newly validated instruments to measure the impact of preference for medication on domains related to falls (physical activity, urinary symptoms, neurocognitive testing) in older adults undergoing treatment with anti-cholinergic medications for overactive bladder. We hypothesize that adults with preference for medications will have greater improvement in physical activity and urinary symptoms, and no difference in neurocognitive testing, than women who do not have preference for medications. This aim will establish if the new instruments are useful in measuring outcomes of preference and physical activity in the clinical setting and also provide preliminary data on the impact of treatment preference and anti-cholinergic medications on physical activity and falls risk in older adults with overactive bladder.

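### Aims 2 and 3 claim 90% power on all 80 enrolled, although both need 8-week data and the plan expects 15% loss; Aim 2 has about 75–78% (two-sided) or 84–86% (one-sided) with 68 evaluable, and Aim 3's figure cannot be verified

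*Combined protocol and SAP*

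**What the plan says.** All three sample-size statements are in Characteristics of the Study Population, Accrual.

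- **Aim 1** is sized on 68 evaluable subjects and then inflated: "Assuming a 15% loss to follow-up, we plan to enroll 80 patients" "to ensure an adequate sample of at least 68 subjects with complete datasets".
- **Aim 2** starts from "We have conservatively assumed that 50% subjects will express preference for medication" and "Prior Penn studies show 56% adherence at 8 weeks in unselected subjects". It takes 80% adherence in those who prefer medication and concludes that "a sample size of 80 subjects will provide 90% power to demonstrate a 30% difference in adherence rates". It gives no alpha and no sidedness.
- **Aim 3** reads "Assuming two-tailed alpha of 0.05, a sample size of 80 subjects will provide 90% power to show a 30% difference in physical activity". It gives no expected proportion for either group.

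Both later aims depend on the 8-week visit. The Aim 2 hypothesis in Objectives is that "adults with preference for medication will have higher adherence to treatment at 8 weeks than adults who do not prefer medication". For Aim 3, the Analysis Plan compares activity at baseline and 8 weeks, and "Improvement in physical activity will be defined as 15% increase in energy expenditure as compared to baseline".

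The Design section mentions intention-to-treat, but for patients taken off fesoterodine who still attend the 8-week visit. No section says how subjects without 8-week data are counted.

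**The concern.** The 15% loss is applied to one aim and left out of the next two, although the same subjects and the same visit supply the data for all three. A 90% figure for 80 subjects is therefore not the power the study expects to have.

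Three further points bear on the same sentences:

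- Without an alpha and sidedness, Aim 2's figure has no single meaning.
- Aim 2's adherence rates do not fit together.
- Aim 3's power cannot be calculated from what is given.

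Aim 2 tests whether the preference instrument is valid, and Aim 3 builds on it. If preference showed no association with adherence, readers would judge that result against a stated 10% risk of missing a 30-point difference. The actual risk is higher.

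**Working it through.** **Inputs.** From Accrual: 80 enrolled; 15% loss, so 80 × 0.85 = 68 evaluable; equal split, so 40/40 or 34/34; adherence 80% with preference; 30-point difference, so 80% − 30 = 50% without preference. Assumption: alpha 0.05 for Aim 2, tried one- and two-sided.

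**Formula.** For n per group, with p̄ the mean of p1 and p2:

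power = Φ( [|p1 − p2| − z·√(2p̄(1−p̄)/n)] / √([p1(1−p1) + p2(1−p2)]/n) )

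This is the pooled form. The unpooled form uses the second square root in both places.

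**Step 1: reproduce the plan's 90% (40/40).** √(2 × 0.65 × 0.35/40) = 0.1067 and √((0.16 + 0.25)/40) = 0.1012.

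- One-sided 5%: (0.30 − 1.645 × 0.1067)/0.1012 = 1.23, power 0.891. Unpooled 0.906.
- Two-sided 5%: (0.30 − 1.960 × 0.1067)/0.1012 = 0.90, power 0.816. Unpooled 0.842.

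The stated 90% appears only one-sided with nobody lost.

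**Step 2: apply the plan's own loss (34/34).** The two square roots become 0.1157 and 0.1098.

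| 80% v 50% | Pooled | Unpooled | Exact power of pooled z-test |
|---|---|---|---|
| 40/40, one-sided | 0.891 | 0.906 | 0.894 |
| 40/40, two-sided | 0.816 | 0.842 | 0.817 |
| 34/34, one-sided | 0.841 | 0.861 | 0.848 |
| 34/34, two-sided | 0.748 | 0.780 | 0.768 |

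For 90% power the study needs 40–42 evaluable per group one-sided or 48–52 two-sided (unpooled to pooled). With 34 per group, 90% is reached only for a gap below 80% of about 32–33 points one-sided or 35.5–37 points two-sided.

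**Step 3: would keeping all 80 help?** Suppose an assumed 15% in each group have no 8-week data and are counted as non-adherent. The rates become 0.80 × 0.85 = 68% and 0.50 × 0.85 = 42.5%. With 40/40, power is 0.75–0.77 one-sided and 0.64–0.66 two-sided, lower than in the complete-case analysis.

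**Step 4: consistency of the Aim 2 rates.**

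- 56% overall, 80% with preference, equal split: 0.5 × 0.80 + 0.5x = 0.56 gives x = 32%, a gap of 48 points. Two-sided pooled power is 0.997 (40/40) or 0.990 (34/34).
- 56% as the comparator: a gap of 24 points, which is a 30% relative difference (24/80). Two-sided pooled power is 0.64 or 0.57; one-sided 0.75 or 0.69.
- The stated 30 points: 50% without preference, which implies 0.5 × 0.80 + 0.5 × 0.50 = 65% overall, not 56%.

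**Step 5: Aim 3.** Read as two proportions 30 points apart, two-sided 0.05, pooled:

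| Assumed rates | 40/40 | 34/34 |
|---|---|---|
| 10% v 40% | 0.888 | 0.830 |
| 15% v 45% | 0.847 | 0.783 |
| 20% v 50% | 0.816 | 0.748 |
| 35% v 65% | 0.776 | 0.705 |
| 55% v 85% | 0.847 | 0.783 |

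With 40/40, 90% needs the lower proportion at about 9–11% or below, or the higher at about 89–91% or above. With 34/34 the limits are about 4–6% and 94–96%.

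**Step 6: the 50% split.** At a fixed total, equal groups are close to the most favourable case. As a sensitivity case only, 68 subjects split 48/20 (80% v 50%, two-sided, pooled) give 0.69 if the larger group prefers medication and 0.65 if the smaller does, against 0.75 at 34/34.

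**The case against.** The strongest reply is that Aim 2 was sized one-sided. Its hypothesis is directional, two-tailed testing is named only under Aim 3, and Aim 1's 90% also reproduces only one-sided (Fisher z, r = 0.72 v 0.50, n = 68: 0.893 one-sided, 0.824 two-sided). On that reading the Aim 2 figure is correct for 80 subjects, and loss costs only about 5 points. This is plausible, and it means that most of the two-sided shortfall comes from sidedness rather than attrition. It does not rescue the claim, because one-sided power after the planned loss is still 0.84–0.86. The plan also does not state the choice.

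Second, the 32% reading gives about 99% power even with 68 subjects. That is true, but it is a 48-point gap and not the difference the plan says it can detect. The shortfall is therefore conditional on the stated 80% and 30 points.

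Third, 68 refers to complete datasets for Aim 1, which needs accelerometer data. Adherence from pill count and MASRI might be available for more subjects, especially with home visits. That is possible, but the plan describes the 15% as loss to follow-up and gives no other number for Aim 2.

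Fourth, no test is named for the adherence comparison, so exact figures are uncertain. This stands. Fisher's exact test would give less: at 34/34, 0.68 two-sided and 0.77 one-sided.

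Fifth, Aim 3 is described as supplying preliminary data, and its sentence may not mean two proportions. That supports calling its power unverifiable, not wrong. The word conservatively may mean only that more than half are expected to prefer medication, so this part is minor.

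**Conclusion.** The concern holds. For the difference the plan names, Aim 2 does not have 90% power after the plan's own 15% loss on either sidedness. The risk of missing a true 30-point difference is about 14–16% one-sided or 22–25% two-sided, against the stated 10%. Loss alone accounts for about 5–7 points; the rest of the two-sided gap is the unstated sidedness. Aim 3's 90% cannot be confirmed or refuted without a base proportion, and for middling proportions it would not hold even with all 80.

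These figures assume alpha 0.05 for Aim 2, equal groups, 80% v 50%, 68 evaluable, and large-sample tests of two proportions. The conflict among 56%, 80% and 30 points needs none of these test assumptions and has to be resolved whichever power is quoted. The point should be fixed: it corrects a stated figure and does not undermine the design.

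**What to change.** Revise the Aim 2 and Aim 3 sentences in Accrual, without adding enrolment:

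- State Aim 2's alpha, sidedness and test.
- Give one adherence rate for subjects without preference and reconcile it with the 56% overall rate.
- Restate Aim 2's power for 68 evaluable. For 80% v 50% this is about 75–78% two-sided or 84–86% one-sided, with 90% only for gaps of about 35.5–37 or 32–33 points.
- Say how subjects without 8-week adherence data enter the analysis.
- Name Aim 3's expected proportion improving in each group and restate its power for 68.
- Drop the word conservatively, and show an unequal split as a sensitivity case.

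The cost is a few sentences and a less favourable stated power. For comparison, keeping 90% for 80% v 50% (pooled formula) would need 84/0.85, about 99 enrolled one-sided, or 104/0.85, about 123 two-sided.
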